**General feedback on VAS scales**

🗣️ *We would also like to have your feedback on the VAS scales overall.*

**31. What do you think of the scales in general?**

- *What did you like/dislike about them?*
- *What did you find easy/difficult?*

**32. Any further comments about the VAS scales?**

## 33. General feedback on real-time data capture ADELPHI VALUES

---

**[TO INTERVIEWER]** The following section should only be asked to participants if they have taken part in the real-time data capture task in addition to the interview.

 *"I would now like to ask you some question about your experience of completing the real-time data capture task*

### 34. Overall how did you find the app task?

- *What did you like/dislike?*
- *What did you enjoy? Was there anything you did not enjoy?*
- *Did you find the app easy or difficult to use? Tell me about that.*
- *Did you find it easy or difficult to submit your responses? Tell me about that.*

### 35. Was it easy or difficult to fit this into your daily routine? Tell me about that.

### 36. Please tell me about your experience of downloading the app?

- *Was this easy or difficult? Tell me about that.*
- *What did you think of the instructions you were provided with to download the app?*

### 37. What did you think of the types of tasks you were asked to complete? Tell me about that.

### 38. What did you think of the ways in which you could respond to tasks? (e.g. video recording, audio recording, photographs and text)

- *Was there a response method that you preferred? If so, why?*
- *Were there any response methods that you did not choose? Tell me about that.*

### 39. What did you think of the number of task you were asked to complete?

- *Were there too many/too few?*
- *On average, how long did each task take you to complete?*

### 40. Is there anything you'd change about the app task at all to make it better?

### 41. How did you find completing the app task before/after your interview?

- *Would you have preferred to take part in the app task before/after your interview instead? Why? Tell me about that.*
- *Would you have answered any of the app tasks/questions differently had you completed the app exercises before/after your interview instead?*

### THANK THE PARTICIPANT FOR HIS/HER PARTICIPATION

Finally I would like to thank you for taking part in this interview and sharing your experiences. If this discussion has given you any concerns about your condition or treatment please contact your doctor.

**Appendix 8: Questionnaires for use in cognitive debriefing interview****QUESTIONNAIRES**

This document contains a number of questionnaires for you to complete, during your telephone interview with Adelphi Values about your nasal polyps. Within this document you will see a series of images of the questionnaire in electronic format, designed for use on a smartphone. Although you will see the questionnaire in this format you will be required to provide your answers on paper in this document by checking the relevant answer.

**IMPORTANT:** This document is for use **DURING** your telephone interview **ONLY**. Please do not complete any of the questionnaires inside this document until you are told to do so during your telephone interview.

[figure not shown]
**Please keep this document and the pre-paid mail return envelope safe until your telephone interview.**

**Following the telephone interview, please mail this document to MedQuest (recruitment agency), using the pre-address and pre-paid mail envelope that has been provided.**

## Questionnaire 1: SNOT 22

---

[figure not shown]
CCI - This section contained Clinical Outcome Assessment data collection questionnaires or indices, which are protected by third party copyright laws and therefore have been excluded.

# Questionnaire 2: Visual Analogue Scales

Instruction: For the following questions you are asked to rate your symptoms on a scale from 0 to 100. At the start of each rating scale you will see a single line (cursor). In electronic form on a smartphone form you would be asked to slide this line to a place on the 0-100 line that represents your answer.

Using a pen/pencil please mark on the 0-100 line using vertical line (|) where you would move the line (cursor) to that represents your answer.

A		Please write which number out of 100 your line represents
		

B	
Please rate your nasal discharge at its worst over the previous 24 hours.
 

Nasal Symptoms Scale

Please rate your nasal discharge at its worst over the previous 24 hours.

0 None 100 As bad as you can imagine

 
Back Next
	
---	--	--

C	
Please rate the feeling of mucus in the throat at its worst over the previous 24 hours.
 

Nasal Symptoms Scale

Please rate the feeling of mucus in the throat at its worst over the previous 24 hours.

0 None

100 As bad as you can imagine

Back Next

	
---	---	--

D	
Please rate your loss of smell at its worst over the previous 24 hours.
 

Nasal Symptoms Scale

Please rate your loss of smell at its worst over the previous 24 hours.

0 None 100 As bad as you can imagine

Back Next

	
---	---	--

E	
Please rate your facial pain or pressure at its worst over the previous 24 hours.
 

Nasal Symptoms Scale

Please rate your facial pain or pressure at its worst over the previous 24 hours.

0 None

100 As bad as you can imagine

Back Next

	
---	---	--

F	
Overall, please rate your nasal polyps symptoms at their worst over the previous 24 hours.
 
 
Nasal Symptoms Scale
 
Overall, please rate your nasal polyps symptoms at their worst over the previous 24 hours.
 
0 100
 
None As bad as you can imagine
 
 
 ← Back Next → 
	
---	---	--

**Thank you for completing these questionnaires**

**Please put this completed document into the provided pre-addressed and pre-paid envelope, and mail it back to MedQuest.**

**Appendix 9: Example real-time data captures questions/tasks**

Example task/question	Comments/Rationale
-----------------------	--------------------

Example task/question	Comments/Rationale

Introductory task/orientation to the device
 
“Using video or audio, please describe your experience of living with nasal polyps.”
	
 
• Prior to commencing the formal app tasks/questions, in order to orient the participant to the device and the response modalities it is recommend that we include an introductory task for completion by the participants.
 

Nasal polyp description task
 
“Please provide a written description of how you would describe nasal polyps to someone who had never heard of the condition.”
	
 
• In addition to understanding the patient experience of nasal polyps, additional value could be gained by getting patient to provide written description of their nasal polyps as if they were describing to someone who doesn’t know what nasal polyps are.
 

Assessment of global severity of nasal polyps
 
“Please rate the severity of your nasal polyps today at their worst.”
	
 
• Asking questions such as these, on a daily basis will allow the day-to-day variability of the global severity of nasal polyps to be reported.
 
• Responses to this daily question could be collected in a number of ways:               
 
○ Categorical response options (e.g. No symptoms through to Very severe)
 
○ Numerical response scale (NRS)
 
○ Implementation of the overall symptom VAS as intended for the Phase III trial. Due to variability in each participant’s screen size of their personal smart phone and the limitations of the app platform it won’t be possible to measure the VAS score as you would on paper or as would be on a provisioned electronic device. Here we would ask the participant to provide a response using a slider option (outlined in the table above) and also ask the participant to provide in a free text box the number the slider position represents.
 
 
 


Assessment of global impact of nasal polyps
 
“Please rate how much your nasal polyps affected your usual activities today”
	
 
• As per global severity assessment, asking questions such as these, on a daily basis will allow the day-to-day variability of the global impact of nasal polyps to be reported.
 
• As described above, categorical, NRS or VAS a VAS sliding response scale could be used to respond to this task. In the case of the sliding scale VAS, a text box will also be provided for the patient to coordinate their sliding scale response to a number. .
 

Assessment of day in the life with nasal polyps
 
“During the study period we would
	
 
• Participants would be asked to complete this question/task once or twice during the study period. Because this main study uses telephone interviews, questions such as these, using video/audio responses, will allow patients to give a more
 

Example task/question	Comments/Rationale

like to understand your experience of nasal polyps over one full day. You can choose any day during the 10-day period you would like complete this task. On your chosen day we would like you think about what you experienced, how it affected you and how you felt. You are encouraged to submit as many video or audio responses as you like as you move through your day.
 
This may include submitting a response first thing in the morning to explain your experience of nasal polyps through the night (e.g. how you slept”.
 
You could submit responses throughout your day as you go about your usual activities, explaining your experience of nasal polyps and how it affects you.
 
You could also submit a response in the evening before bed describing your day’s experience with nasal polyps.
 
These are just suggestion and you can submit any responses that you feel documents your experiences that day”
	
detailed description of their symptom and daily life experiences with nasal polyps and allow the researchers at AV further insight into their experience of the disease.

Example task/question	Comments/Rationale

Assessment of treatment experiences
 
“Please take a photo(s) of the medications or remedies you use for your nasal polyps and provide a short text caption/description about what is shown in the photo(s) and what it means to you).”
 
“Using video, audio or text response please describe which of these treatments (if any) you used today?
 
What are the benefits you have seen today from these treatments?
 
Is there anything you have disliked about your treatments today?”
	
 
• Treatments and surgical experiences and decisions for nasal polyps was discussed in both the qualitative literature and the patient blogs reviewed as part of an earlier nasal polyps literature review for GSK, and is included in the preliminary conceptual model. It is suggested that further detail regarding treatments and surgical decisions for nasal polyps is investigated using the app task.
 

Capturing feelings/emotions
 
“During the 10-day period take photos of things that describe your experience of nasal polyps that day and how you felt. You can submit as many photographs as you like. For each photo submitted please provide a short text caption/description about what is shown in the photo and what it means to you.”
 
“For each photo provided, please rate the importance of this photograph to you?” Why did you give it this number?
	
 
• A technique that has been utilised successfully in other AV studies is the implementation of creative exercises. Here, patients could be fielded creative question to ‘take a photo that best describes your feelings towards your nasal polyps today, and use the caption to explain why you chose this photo’. Again, this requires patient to consider their condition and experience of it differently and may allow for interesting insight. As part of this process patient could be asked to rank the importance of the photos submitted using a sliding scale. Ranking criteria could be discussed and drafted with input from GSK
 

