#### **3.2.1.1 Inclusion Criteria**

Participants will be required to meet the following inclusion criteria to be eligible for inclusion in the study.

1. Participant has a clinical diagnosis of **bilateral nasal polyps** as diagnosed by endoscopy or CT scan;
2. Participant is aged 18 or over;
3. Participant has severe nasal polyps symptoms defined as a patient-reported nasal obstruction VAS score of >5 (Appendix 1);
4. Participant has had at least **one previous surgery in the past ten years** for the **removal of nasal polyps**. Surgery in this case is defined as any procedure involving instruments with resulting incision and removal of polyp tissue from the nasal cavity (polypectomy);

5. Participant is currently an eligible candidate for polypectomy defined by:

a) An overall patient-reported VAS symptom score of  $>7$ . (**Appendix 2**), **AND**

An endoscopic bilateral nasal polyp score of at least 5 out of a maximum score of 8 (with a minimum score of 2 in each nasal cavity). (

- b) Appendix 3);
- 6. Participant has symptoms consistent with chronic rhinosinusitis;
- 7. Participant is currently received intranasal corticosteroids for the management of their nasal polyps;
- 8. Participant is willing to participate in the study and provide informed consent;
- 9. Participant is an English speaker and is able to read, write and fully understand the English language;
- 10. Participant is willing to and able to attend and participate in a 120-minute interview to discuss their experiences of nasal polyps and obtain their feedback on several symptom/impact questionnaires.

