### **Real-time data capture**

All 20 US patients will be invited to take part in an app-based real world data capture activity. It is anticipated that of the 20 interview participants, a sub-set of ten will meet the inclusion criteria for this task. Five of the ten participants (50%) will take part in the app task prior to their interview and the remaining five participants (50%) will take part in the app task following their interview. Eligible participants will receive instruction and supporting documentation on how to download and access the application via their smartphone or tablet. Participants will be required to take part in the real-time data capture exercise over the course of 10 days and during this time a series of approximately 10 questions/tasks will be fielded to participants via the application to explore the experience of the symptoms, HRQoL impacts and treatment of nasal polyps and any day-to-day variability that exists these experiences in 'real time'. Some questions/tasks may be issued daily over the 10 days and others may be issued once. Examples of the types of questions that might be asked to participants via the application are documented in Appendix 9. Each task will take no longer than 5-10 minutes to complete and participants will be able to provide responses to the questions/tasks fielded to them using a variety of methodologies including video, audio, text and photographic responses.

Once recorded, the participants can submit their responses via Wi-Fi or 3/4G and they will become immediately viewable on a response dashboard for the study researchers to track and analyses. The AV research team would be able to interact with participants via the dashboard (e.g. add new tasks, send reminders to complete a task), monitor compliance and review and run reports on received responses to questions/tasks. All data from the dashboard would be downloaded and stored by Adelphi Values. As part of this process any video or photographic data whereby the participant's face was visible would be blurred/redacted.

Germany participants will not be invited to take part in the real-time data capture app task.

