### The role of the interviewer is to **inquire** and **support**:

Do not give your own point of view

Be patient and accept silence during open-ended questioning to make sure the patient has time to think about her/his response

Help the patient stick to the topics intended in the guide (but not necessarily in the order presented in the guide)

Help the patient avoid repeating himself or herself

Help the patient cross-reference and make connections that they would not do spontaneously

Ask the patient to clarify any comments that you are not certain you understood and for the benefit of the recording

Ask the patient to explain any vague reference or comment that is pertinent to the research question

**Most importantly:** avoid biasing or leading the patient

**As much as possible your questions should be open-ended and general rather than specific – use suggested probes to follow-up on topics of interest if not adequately discussed in response to the open questions.**

**It is very important that you do not lead the patient with your questions or remarks.** Ask all questions in as open-ended a manner as possible; take care not to bias the patient's response one way or the other. Below for most questions, we have provided a number of possible probes that should help the patient explain his or her thinking when s/he is talking about the topics of interest. These probes are

ADELPHI VALUES

**optional** and do not have to be asked if, when asked the initial question, the patient provides a fully elaborated response and addresses the topics noted in the probes. The probes are only provided for use when the patient finds it difficult to answer your questions, if s/he is reluctant to speak at length about experiences or if key topics of interest have not been elicited spontaneously. You may have to invent your own probes or reword the probes indicated in the interview guide; this is fine. As a fully trained and experienced interviewer we rely on your judgment as to when more information is required from the patient and for you to probe as appropriate.

POSSIBLE NON-LEADING PROBES MIGHT INCLUDE:

- Can you describe exactly how that feels?
- Tell me more about that.
- How does that affect you?
- Can you talk more about \_\_\_\_\_?
- How often does that happen?
- How long does that last?
- Is there anything that makes it better or worse?

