**23. Tell me about your experience of having nasal polyp surgery?**

- *What effect did surgery have on your symptoms and any impacts you experienced?*
- *How did having the nasal polyp surgery impact your life?*
- *What were the positives of having surgery (if any)?*
- *Were there any negatives or drawbacks of having surgery?*
- *Would you choose to have additional surgeries to remove your nasal polyps? Why/why not?*

**24. How have the treatments that you have taken for your nasal polyps impacted your life (if at all)? This may include prescribed, over-the-counter and alternative treatments.**

- *What was good about these treatments?*
- *What was bad about these treatments?*

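### The example app question on treatment benefit presupposes that there was one; neutral, symmetric wording in the final app script would remove a minor prompting risk at almost no cost

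*Combined protocol and SAP*

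**What the plan says.** The treatment task in Appendix 9 first asks for photographs of medications or remedies. Three prompts follow:

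- Use: "please describe which of these treatments (if any) you used today"
- Benefit: "What are the benefits you have seen today from these treatments"
- Dislike: "Is there anything you have disliked about your treatments today"

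The status of this wording is given in Section 3.3 (Real-time data capture): "Examples of the types of questions that might be asked to participants via the application are documented in Appendix 9". The same section describes researcher contact during the task: "The AV research team would be able to interact with participants via the dashboard (e.g. add new tasks, send reminders to complete a task".

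Appendix 7 instructs interviewers: "Ask all questions in as open-ended a manner as possible". Its probe on surgery, under Q23, reads: "What were the positives of having surgery (if any)".

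Section 2.2 names treatment, with symptoms and quality-of-life impacts, as a topic of the app task. Section 4 says that app responses are coded in the same manner as the interview transcripts and that both sets of results inform the conceptual model.

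**The concern.** The benefit prompt is leading. It does not ask whether a benefit occurred; it asks what the benefits were. The negative side is put as an open yes/no question, so the pair is lopsided. Someone who felt no effect, or felt worse, has to reject the premise before answering, and no interviewer is present at that moment to rephrase it.

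What is at stake is the balance of the treatment material from the app. If some participants name a benefit because one was asked for, or do not mention that nothing changed, the coded data will under-represent same-day experience of no effect. Those data go into the conceptual model alongside the interview findings.

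**Working it through.** No arithmetic applies. The study has no hypotheses (Section 3.5) and no formal endpoints (Section 3.3.1), and the documents give no figure on this point. The check is a comparison of wording and of the procedures around it.

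**1. Within the task.** The use prompt carries the qualifier 'if any'. The benefit prompt, which comes next, drops it. The dislike prompt is conditional in form. A participant who has just reported using nothing still meets the benefit prompt unqualified, because the example shows no branching.

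**2. Against the interview guide.**

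| Item | Qualifier on the positive side | Negative side |
|---|---|---|
| App benefit prompt (Appendix 9) | None | Open question on dislikes |
| Q23 surgery probe (Appendix 7) | 'If any' | Open question on drawbacks |
| Q24 treatment probe (Appendix 7) | None in the probe, but the stem says 'if at all' | Paired directly with what was bad |

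The Q24 probe on what was good is itself unqualified. Its neutrality comes from the stem and the paired probe. The app prompt is preceded by a qualifier on use, but it has no neutral stem about effect.

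**3. Whether no benefit is a plausible answer.** Section 3.2.1.1 item 7 reads: "Participant is currently received intranasal corticosteroids for the management of their nasal polyps". Item 5 also requires an overall symptom VAS above 7, a level that Section 1 classes as severe, and an endoscopic polyp score of at least 5 out of 8. Participants are therefore on treatment and still severely symptomatic, so a report of no benefit today is realistic. These criteria do not show how common it would be.

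**4. Whether a planned safeguard catches it.**

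- Section 5 offers probes or examples to participants who are unsure how to respond. A participant who accepts the premise and names a benefit is not unsure.
- The dashboard lets researchers see and follow up answers, but no rule directs them to look for this.
- The post-task questions (Appendix 7, Q34 to Q41) cover the experience of using the app. They do not return to the content of the treatment answers.
- The non-leading instruction is addressed to interviewers. Nothing in the documents extends it to app wording.

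The presupposition and the asymmetry are therefore confirmed, and no safeguard is aimed at them.

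**The case against.** The strongest reply is that this is a comment on draft wording in a small supplementary task. Most of that reply stands.

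- **Status.** Appendix 9 is a set of examples, and the research team is responsible for the final app content (Section 3.3). The prompt is not part of a fixed instrument.
- **Open answers.** Participants reply by video, audio or text and can simply say there was no benefit. Dislikes are asked about next.
- **Follow-up.** Responses are visible at once on the dashboard, new tasks can be added, and participants can be reached by app, email or telephone (Section 5). A route to clarification exists, though it is not targeted at this problem.
- **Other sources.** The app supplements the interview (Section 2.2). All app participants are also interviewed, and numbered questions are posed to everyone. Q24 asks how treatments have affected life, if at all, and Q13 and Q14 ask what makes matters better or worse. Experience of no effect has a more neutral place there, although not as a same-day report.

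What survives is narrow. The same-day reports are what the app adds to the interview, and for those the only treatment wording in the documents assumes benefit.

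**Conclusion.** The point holds as a minor, free improvement. The example benefit question is leading by the study's own standard. It may prompt benefit statements and leave same-day no-effect answers unelicited in a ten-person task. The size cannot be estimated from the documents. The conclusion assumes that the final app script would carry the example wording over unchanged, which the documents neither state nor rule out.

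A reader might infer more, and the documents do not support it:

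- **That the question creates the benefit statements, or that nobody can correct it.** Answers are open and researchers can follow up. What can be said is that statements may be prompted and that no interviewer is present when the question is answered.
- **That no effect is the commonest experience in this sample.** Being symptomatic enough to enter the study does not show that treatment gives no daily relief.
- **That the bias can be sized at 10 percentage points per person.** One of ten participants is 1/10 = 10%, but this is only the weight of one person. No share reporting benefit is a planned output. Section 4 allows frequencies to be reported but rules out quantitative analysis of them.

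**What to change.** When the app script is finalised, replace the benefit and dislike prompts with a neutral, symmetric pair, for example:

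- *What effect, if any, did these treatments have on your nasal polyps symptoms today (better, no change, worse)? Please describe.*
- *What, if anything, did you like or dislike about your treatments today?*

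At minimum, add 'if any' to the benefit question. That alone removes the presupposition.

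No conditional display is needed, because the qualifier also covers a participant who used nothing. No separate coding rule is needed either: the synopsis says that the code list is updated iteratively, so a no-effect code can be added if such answers appear. The cost is two sentences of app wording, with two prompts still replacing two.
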